4.2. Secondary specific objectives

- To assess differences in other mosquito infectivity parameters (mosquito infection rate, change in infection rate, infectivity to mosquitoes, and oocyst density) following treatment with ASAQ, ASAQ-PQ, AL, ALAQ and ALAQ-PQ in children and adults at all feeding timepoints compared to pre-treatment (day 0) and between treatment matched arms (ASAQ vs ASAQ-PQ, AL vs ALAQ, ALAQ vs ALAQ-PQ).
- To assess differences in gametocyte parameters (prevalence, density, circulation time, area-under-the-curve, sex-ratio) following treatment with ASAQ, ASAQ-PQ, AL, ALAQ and ALAQ-PQ in children and adults at all feeding timepoints compared to pre-treatment (day 0) and between treatment matched arms (ASAQ vs ASAQ-PQ, AL vs ALAQ, ALAQ vs ALAQ-PQ).
- To assess differences in safety parameters (AE frequency, Hb density, median drop in Hb) following treatment with ASAQ, ASAQ-PQ, AL, ALAQ and ALAQ-PQ in children and adults at all feeding timepoints compared to pre-treatment (day 0) and between treatment matched arms (ASAQ vs ASAQ-PQ, AL vs ALAQ, ALAQ vs ALAQ-PQ).
- To assess differences in biochemical parameters (ALT, CBC, Creatinine) following treatment with ASAQ, ASAQ-PQ, AL, ALAQ and ALAQ-PQ in children and adults at all feeding timepoints compared to pre-treatment (day 0) and between treatment matched arms (ASAQ vs ASAQ-PQ, AL vs ALAQ, ALAQ vs ALAQ-PQ).

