7.2. Secondary outcome measures

- Median within person percent change (presented as percent reduction) in mosquito infection rate from baseline to all feeding time-points, with comparison within and between arms.
- Median mosquito infection rate at all feeding time-points, with comparison within treatment arms compared to baseline, and between arms.
- Infectivity to mosquitoes at all feeding time-points, with comparison within treatment arms compared to baseline, and between arms.
- Mean oocyst intensity (in all/all infected mosquitoes) at all feeding time-points, with comparison within treatment arms compared to baseline, and between arms.
- Male and female gametocyte prevalence at all time-points, determined by microscopy or molecular assays, with comparison within treatment arms compared to baseline, and between arms.
- Male and female gametocyte density at all time-points, determined by microscopy or molecular assays, with comparison within treatment arms compared to baseline, and between arms.
- Male and female gametocyte sex ratio (proportion male) at all time-points, determined by microscopy or molecular assays, with comparison within treatment arms compared to baseline, and between arms.
- Gametocyte circulation time (cumulative), determined by microscopy or molecular assays, compared between treatment arms.
- Gametocyte area under the curve (cumulative), determined by microscopy or molecular assays, compared between treatment arms.
- Asexual and total parasite prevalence at all time-points, determined by microscopy or molecular assays, with comparison within treatment arms compared to baseline, and between arms.
- Asexual and total parasite density at all time-points, determined by microscopy or molecular assays, with comparison within treatment arms compared to baseline, and between arms.
- Haemoglobin density at all time-points, with comparison within treatment arms compared to baseline, and between arms.
- Median within person percent change (presented as percent reduction) in haemoglobin density from baseline to all time-points, with comparison within and between arms.
- The frequency and prevalence of adverse events (all AE's, treatment related AE's, and haematological AE's) observed up to and including day 2, 7, and 14 post-treatment, and at all timepoints.

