9. SAFETY EVALUATION

The major safety endpoint is haemolysis. For this reason, haemoglobin will be measured before treatment, at days 1, 2, 7, 14, 21, and 28. Previous studies have shown that highest haemoglobin fall related to drug induced haemolysis can be detected within 7 days after treatment. In addition at 24 hours, and subsequent days of follow up, a questionnaire

assessing adverse events (AE) will be carried out. All participants will have access to contact study medical staff 24 hours a day and medical facilities that can give safe blood transfusions. Participants who require blood transfusions will be hospitalised at the district hospital in Ouelessebougou or referred to the University hospitals in Bamako for proper management. Additional safety precautions due to the small risk of transient haemolysis in this population will include the performance of clinical examinations and monitoring for adverse events (AE) at all sampling time points, carefree of charge to all participants throughout the duration of follow-up.

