11.1. Analysis plan

Mosquito infectivity will be assessed at three levels: the mean number of oocysts in a sample of mosquitoes (i.e. oocyst intensity), the proportion of mosquitoes infected with any number of oocysts (i.e. mosquito infection rate), and the infectivity of the study participant to any number of mosquitoes (i.e. infectivity to mosquitoes). The primary outcome measure will be the percent change in mosquito infection rate within each arm by day 2 compared to baseline, with other time-points of infectivity assessments as secondary outcomes. Percent change will be reported as percent reduction (with 100% as total reduction of transmission, and negative values as enhanced transmission). Other secondary transmission outcomes are as described in the 'Objectives' section above. Some exploratory objectives may be published separately from the main primary/secondary outcomes.

Statistical analysis will be conducted using the most recent STATA and SAS versions (16.0 and SAS version 9.4 at time of writing). Mosquito infection data will be analysed at time-points after baseline only for those individuals who are infectious at baseline, although the data and analyses from all enrolled individuals will be published in the appendix for completeness. Individuals will be classified as infectious to mosquitoes if they infect at least 1 mosquito, with any number of oocysts. Infectivity to mosquitoes and parasite/gametocyte prevalence will be compared within and between treatment arms using generalised linear models (family: binomial, z-score, co-efficient with 95% CI) or fishers exact tests. Absolute haemoglobin density and percent change in haemoglobin density (relative to baseline) will be compared using paired t-tests (t-score for difference compared to day 0) and two-way t-tests (t-score for difference between ACT matched treatment groups at each time-point). The proportion of gametocytes that are male will be calculated for all values with total gametocyte densities of 0.2/ μ L and over. Gametocyte circulation time will be calculated to determine the average period (in days) that a mature gametocyte circulates in the blood prior to clearance, using a deterministic compartmental model that assumes a constant rate of clearance and has a

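### The haemoglobin change outcome is defined as a median but tested with t-tests on means, so the reported effect and its p-value describe different quantities

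*Protocol*

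**What the plan says.** - Section 9 sets the role of haemoglobin: "The major safety endpoint is haemolysis". For that reason "haemoglobin will be measured before treatment, at days 1, 2, 7, 14, 21, and 28". It adds that the "highest haemoglobin fall related to drug induced haemolysis can be detected within 7 days after treatment".
- Section 4.2 lists among its objectives differences in "safety parameters (AE frequency, Hb density, median drop in Hb").
- Section 7.2 has two haemoglobin outcomes. One is haemoglobin density at every time-point, with no summary statistic named. The other is "Median within person percent change (presented as percent reduction) in haemoglobin density from baseline to all time-points, with comparison within and between arms".
- Section 11.1 gives the tests: "Absolute haemoglobin density and percent change in haemoglobin density (relative to baseline) will be compared using paired t-tests" against day 0, and by two-group t-tests between ACT-matched arms at each time-point. Later in the same section, Wilcoxon signed-rank and rank-sum tests are assigned to all other quantitative data. The text therefore places haemoglobin outside the rank tests.
- The synopsis states that G6PD status will not be tested. Section 5.1 puts the local frequency of deficiency at 10 to 15%. Section 7.3 lists G6PD genotyping among the exploratory outcomes only.

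**The concern.** A t-test is inference about a mean. If the results table shows a median change and the adjacent p-value comes from a t-test, the p-value does not belong to the number beside it, and a confidence interval from the t-test would not be an interval for the median. In many trials the difference would be cosmetic, because the two summaries nearly coincide when the whole arm shifts together.

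That is not the pattern to expect here. Section 12.2.2 attributes primaquine haemolysis to G6PD-deficient individuals, so any drug-related fall would be concentrated in a few people. A few large falls pull a mean and leave a median almost where it was. The summary named in the outcome is thus the less sensitive of the two to the harm being monitored, while the test looks at the more sensitive one. A reader could see a small median fall and take it as the size of the effect that was tested.

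**Working it through.** The protocol gives no expected value, SD or power for haemoglobin, so there is no figure of its own to reproduce. The 88% power in section 5.4 concerns mosquito infectivity.

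**Inputs from the protocol.** 20 participants per arm (Table 1, section 5.4); G6PD deficiency 10 to 15% (section 5.1); no G6PD test at entry (synopsis).

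**Assumed.** The SD of percent change is 5 or 8 percentage points. The extra fall in susceptible primaquine recipients is 20 or 30 points. The susceptible share equals the stated deficiency frequency.

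**Step 1: susceptible participants per arm.** The expected number is 20 × 0.10 = 2 to 20 × 0.15 = 3. From the binomial distribution, the chance of at least one is 1 − 0.90^20 = 0.88 to 1 − 0.85^20 = 0.96. The chance of 10 or more, enough to control the median of 20, is below 0.0003 even at 15%.

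**Step 2: effect on the mean.** If k of 20 fall a further f points, the mean shifts by k × f / 20.
- k = 3, f = 20: 3 × 20 / 20 = 3.0 points.
- k = 2, f = 30: 2 × 30 / 20 = 3.0 points.

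**Step 3: effect on the median.** The median of 20 is the average of the 10th and 11th ordered values. If 3 participants move to the bottom, these become the 7th and 8th of the other 17. Their expected normal scores are about −0.29 and −0.15, average −0.22, so with SD 5 the shift is 0.22 × 5 = 1.1 points. With 2 participants they are the 8th and 9th of 18, average score about −0.14, giving 0.14 × 5 = 0.7 points. Once the susceptible participants lie below the middle of the arm, the depth of their fall no longer affects the median.

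**Step 4: simulation of 20 v 20.**

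| SD | Susceptible | Extra fall | Mean difference | Median difference |
|---|---|---|---|---|
| 5 | 3 of 20 | 20 points | 3.0 | 1.1 |
| 5 | 2 of 20 | 30 points | 3.0 | 0.7 |
| 8 | 3 of 20 | 20 points | 3.0 | 1.7 |

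The simulation agrees with steps 2 and 3. The two-group t-test has about 9 to 17% power in these settings.

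**Step 5: one arm by hand.** If 17 participants fall 3% and 3 fall 30%, the median is 3.0% and the mean is (17 × 3 + 3 × 30) / 20 = 141 / 20 = 7.05%.

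**Step 6: would a largest-fall comparison do better?** Take each participant's largest fall over days 1, 2 and 7. Assume 3 of 20 are susceptible, with a fall of 1.0 or 2.5 g/dL and measurement and between-person SDs of 0.4 or 0.5 g/dL each. A t-test on the largest fall then has about 6 to 15% power, and the single-visit t-tests about 5 to 16%. Neither is strong.

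**The case against.** The strongest reply is that this is a label in one secondary outcome. Section 7.2 also lists absolute haemoglobin without calling it a median, and the t-test on that outcome is coherent. The t-test on percent change already targets the tail-sensitive quantity. Section 12.2.2 cites two trials designed around G6PD-deficient individuals that found no clinically relevant haemoglobin reductions with single low-dose primaquine, so falls as large as those assumed above may not occur. All of this stands, and it limits the size of the point. It does not remove the conflict between sections 4.2 and 7.2 on one side and 11.1 on the other.

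Three stronger readings are tempting and are not supported.

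- **A reader might infer that haemolysis could go unseen because every haemoglobin outcome is tied to a visit.** The plan has measures that cut across visits. Section 7.2 counts haematological adverse events cumulatively to days 2, 7 and 14 and overall. Section 9.1.1 records clinically significant laboratory abnormalities as adverse events. The fall of more than 40% in section 9.3 is only the severe category. Table 5 has signs of haemolysis assessed at every visit, and section 9.6 sends adverse events and haemoglobin to day 14 to the DSMB monthly.
- **A reader might infer that the largest fall should lead the haemolysis comparison.** Section 9 places the largest fall within 7 days, and haemoglobin is measured on days 1, 2 and 7, so the window is covered. With 2 to 3 susceptible participants per arm the largest-fall test has little power (step 6). Its absence contradicts nothing in the protocol.
- **A reader might infer that a significant p-value would often contradict the reported median.** In the simulated settings, opposite signs together with p < 0.05 occurred in at most 0.04% of trials. The problem is a mismatched estimate, not a reversed conclusion.

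**Conclusion.** The conflict is in the text and needs no assumption: the outcome is a median, the test is of means, and section 11.1 excludes haemoglobin from the rank tests. Its practical size does rest on assumptions. With 2 to 3 of 20 susceptible, extra falls of 20 to 30 points and an SD of 5 to 8 points, the median difference is 0.7 to 1.7 points where the mean difference is 3.0. If nobody falls, or the whole arm shifts together, the two agree and nothing is lost. The point is modest but worth correcting, because it concerns the stated major safety endpoint and the named summary is the one that a small susceptible subgroup barely moves. It does not show that the safety monitoring would miss severe haemolysis.

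**What to change.** 1. In sections 4.2 and 7.2, state the haemoglobin change outcome as the mean within-person percent change from baseline.
2. In section 11.1, report each arm's mean and the mean difference between ACT-matched arms with its 95% CI, from the same t-test that gives the p-value. Keep the median as description only.
3. Optionally, as a supporting descriptive result, show each participant's largest percent fall from day 0 through day 7 by arm, with mean, range and individual values. Compare it between ACT-matched arms and not against zero, because taking the worst of several readings gives a fall from noise alone. It should not be the lead comparison.

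Keeping the median and moving haemoglobin to the Wilcoxon tests would bring the wording closer together, but it would retain a summary that 2 or 3 large falls hardly move.

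The cost is a change of wording in three sections and, if item 3 is taken up, one derived variable. No new visit, sample or change to clinical management is needed.

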7.3. Exploratory outcomes

- Parasite genotype and transcriptional analysis at baseline and at post-treatment timepoints, both for blood stage parasites and oocysts.
- Plasma biomarkers (antibodies and parasite protein) at baseline and at post-treatment timepoints.
- Association between gametocyte density and mosquito infection rates per study drug and time-point, to examine evidence for loss in gametocyte fitness/sterilization.
- Human genotype analysis at baseline (G6PD, CYP2D6, HBB)
- ALT/Creatine density at all time-points with comparison within treatment arms compared to baseline, and between arms.
- Gametocyte density, mosquito infection rate and mean oocyst intensity before and after MACS, for within treatment arm comparison to baseline and comparison between treatment arms.

Table 5. Outcome measures

Outcome measure	Day 0	Day 1	Day 2	Day 7	Day 14	Day 21	Day 28
Mosquito infectivity	*		*	*	*	**	**
Asexual parasite prevalence & density	*		*	*	*	*	*
Gametocyte prevalence, density, sex ratio, genotype	*		*	*	*	*	*
Biochemistry (ALT/Creatinine)	*		*		*		
CBC	*		*		*		
Haemoglobin	*	*	*	*	*	*	*
Safety assessment: signs of haemolysis	*	*	*	*	*	*	*
Safety assessment: Adverse Events	*	*	*	*	*	*	*
Plasma biomarkers	*		*	*	*	*	*
Mosquito infectivity after MACS	*		*				

** Mosquito infectivity assays will be performed at day 21 for any individuals infectious at day 7 or 14; and at day 28 for any individuals infectious at day 14 or 21.

8. PROCEDURES

8.1. Informed consent

Consenting procedures will vary based on age of the potential participant. Participants aged 18 years and above will provide informed consent. For participants under 18 years of age we will seek parental consent. In addition to parental consent, assent will be sought for children aged 10-17 years. The Ethics committee in Mali does not require that participants under the age of 10 provide assent. The written, informed consent procedure will be conducted in French or in a local language understood by subject as described in the information and consent form.

The informed consent document will be used to explain the risks and benefits of study participation to the participant and in the case of participants < 18 years, the participant's parent in simple terms before the subject is enrolled in the study. The informed consent document contains a statement that the consent is freely given, that the subject is aware of the risks and benefits of entering the study, and that the subject is free to withdraw from the study at any time. Written consent must be given by the participant or the participant's parent, after the receipt of detailed information on the study. The informed consent form will be signed and personally dated by the participant or the participant's parent and the person who conducts the informed consent discussion. The original signed informed consent form will be retained in the participant's chart and another copy will be provided to him. A participant who is unable to read or write will place an imprint of his finger in place of a signature; in addition, an independent witness will sign the consent form to attest that the information in the consent form was orally conveyed to the participant. Specific consent will be provided for sharing samples and anonymized data to collaborating institutes outside Mali and for sharing data in anonymous form on a digital repository.

8.2. Study procedures

Participants who agree to participate and provide written, informed consent will be assessed for the presence of sexual blood stage parasite with a thick blood film. Individuals with ≥ 16 gametocytes/ μL will go through additional screening for eligibility including haemoglobin measurement, CBC, assessment of the renal and liver functions and pregnancy tests. Recruitment will continue until 100 infected individuals with microscopically detectable *P. falciparum* gametocytes ($\geq 16/\mu\text{L}$) are recruited and randomised. Individuals with symptomatic malaria will not be enrolled in the study and will be treated with artemether + lumefantrine, the standard treatment for uncomplicated malaria as per the Ministry of Health policy in Mali. Individuals screened found with other acute diseases will also be treated according to the standard of care in Mali. Those with chronic disease will be referred to the district hospital for further evaluation and management.

Eligible patients will then be randomized (see below under randomization procedure) to one of the treatment groups, and drugs will be administered. In case of vomiting within 30 minutes after drug intake, the drugs will be re-administered once.

The participants will be compensated for any travel costs and for work loss income. Participants will be followed for 28 days as described in **Table 6** (below). Single venous draws or finger pricks will be used.

Any individuals determined to have an adverse event (haemolytic or otherwise) will be treated in accordance with national guidelines and best practice and will be withdrawn from the study at the discretion of the study clinician.

Table 6. Sampling framework for study participants

Required vacutainer	Time of sampling (d = day)	Required volume (mL)	Day 0	Day 1	Day 2	Day 7	Day 14	Day 21	Day 28
			V	C	V	V	V	V	V
Heparin (2-5mL)	Mosquito infectivity	2	*		*	*	*	**	**

	MACS	3	*		*				
EDTA (0.05-3.4mL)	Blood in RNA protect for RNA analysis/parasite genotyping	0.7	*		*	*	*	*	*
	Blood smear for asexual parasite and gametocyte density	0.1	*		*	*	*	*	*
	Filter paper blood spots	0.05	*		*	*	*	*	*
	Haemoglobin	0.05	*	*	*	*	*	*	*
	Plasma	1	*		*	*	*	*	*
	CBC	0.5	*		*	*	*		
	Human genotyping	1	*						
SST (0.8 mL)	Biochemistry	0.8	*		*	*	*		
	Maximum total Volume of blood sampled (mL)	38.65	9.2	0.05	9.2	6.2	6.2	3.9	3.9

\$ V denotes venous blood sampling and C denotes capillary sampling from a finger prick.

** Denotes volume taken for any individuals infectious at day 7 or 14 (day 21) and for any individuals infectious at day 14 or 21 (day 28).

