5.1. Study site

The Malaria Research and Training Centre (MRTC) in Bamako, Mali will use the field site of Ouelessebougou for recruitment. The MRTC has the unique position of being one of very few sites in Africa that can study malaria transmission endpoints. Since 2013 the MRTC successfully carried out similar trials at this site with great success, in collaboration with the University of California San Francisco, the London School of Hygiene and Tropical Medicine and the Radboud University Medical Center, Nijmegen, the Netherlands. In the 2013-2014 study, the MRTC demonstrated the efficacy of SLD PQ of doses of 0.125mg/kg or greater in combination with dihydroartemisinin-piperaquine for blocking *P. falciparum* transmission safely in G6PD normal Malian males from the age of 10-50 years [8]. MRTC has already established all the assays required for the study described in this protocol.

The MRTC is experienced in conducting Good Clinical Practice (GCP) compliant clinical trials including phase 1, 2, 3 and 4 of malaria vaccine and drug studies. Ouelessebougou village has been conducting ongoing clinical research since 2008 and is endemic for malaria with marked seasonality and a high burden of malaria in both children and adult populations. In recent years the prevalence of *P. falciparum* malaria in children under 5 years of age has ranged between 14% and 54% during the transmission season. The frequency of G6PD deficiency is in the range of 10 to 15%.

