9.3. Haematological severe AE

A haematological severe AE is defined as a drop in Hb density of >40% from baseline. These will be reported separately in the data safety and monitoring reports and in any resulting publications, due to their potential linkage with PQ treatment.

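### Section 8.2 lets an adverse event, haemolysis included, end study follow-up, so later haemoglobin can go missing because of the outcome it measures

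*Protocol*

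**What the plan says.** Protocol section 8.2 sets the rule. It covers "Any individuals determined to have an adverse event (haemolytic or otherwise"), who will be treated under national guidelines and "will be withdrawn from the study at the discretion of the study clinician". What ends is study participation. No criteria are given, and nothing is said about measurements after withdrawal.

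Section 9 states the safety aim: "The major safety endpoint is haemolysis". It schedules follow-up accordingly: "haemoglobin will be measured before treatment, at days 1, 2, 7, 14, 21, and 28". It adds that the "highest haemoglobin fall related to drug induced haemolysis can be detected within 7 days after treatment".

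Section 7.2 lists as secondary outcomes the haemoglobin level and the median within-person percent change "in haemoglobin density from baseline to all time-points, with comparison within and between arms". Section 9.3 adds a threshold event: "A haematological severe AE is defined as a drop in Hb density of >40% from baseline". Section 11.1 compares haemoglobin with day 0 by paired t-tests, and between ACT-matched arms by t-tests at each time-point.

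On who might haemolyse, section 5.1 says "The frequency of G6PD deficiency is in the range of 10 to 15" per cent. Section 2 says that G6PD status is not tested at entry; sections 7.3 and 10.2 provide for genotyping as an exploratory measure.

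**The concern.** A participant whose haemoglobin starts to fall on day 1 or 2 is the person the haemolysis endpoint is meant to follow, and is also the person section 8.2 allows to leave. Withdrawal at that point can come before the nadir. The day 7 value, whether the fall goes on to pass 40%, and the recovery to day 28 may then never be measured.

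Missingness of this kind depends on the outcome. If those who leave have larger falls than those who stay, the arm looks safer than it was at every later visit. An analysis plan can choose how to handle missing values, but it cannot recover measurements that were never taken, and any model for them would rest on assumptions the data cannot test. The DSMB is affected too, since its monthly reports (section 9.6) carry haemoglobin up to day 14.

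Whether the loss could differ by arm depends on whether the deciding clinician knows the allocation, and the protocol contradicts itself on this. Section 5 blinds all staff but the pharmacist, section 5.3 exempts the pharmacist and the clinician, and section 8.4 blinds the treating physician.

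**Working it through.** **Does another section cure the problem?**

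- Section 9 promises monitoring and care for the duration of follow-up. Withdrawal ends follow-up, so this does not reach a withdrawn participant.
- Sections 9.2 and 9.5 put the event on the case report form with intensity, duration and outcome. That keeps the event but schedules no further haemoglobin.
- Section 9.6 reports discontinuations with reasons to the DSMB. That counts the loss but does not prevent it.

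None of them keeps a withdrawn participant on the haemoglobin schedule.

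**How many could be concerned?** Inputs: 20 per arm (Table 1) and 10 to 15% G6PD deficiency (section 5.1).

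- Expected per primaquine arm: 20 × 0.10 = 2 to 20 × 0.15 = 3.
- Chance of at least one in an arm: 1 − 0.90^20 = 0.878 to 1 − 0.85^20 = 0.961.

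These are counts of deficient people, not of people who will haemolyse or be withdrawn.

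**How far could the mean move?** The protocol states no figure to reproduce here, so this is an illustration. Let k of 20 participants have an excess fall of e g/dL over the rest, and let all k leave before a visit. The full-arm mean fall exceeds the observed mean fall by k × e / 20. Both k and e are assumptions.

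| k lost | e = 1 g/dL | e = 2 g/dL | e = 3 g/dL |
|---|---|---|---|
| 1 | 0.05 | 0.10 | 0.15 |
| 2 | 0.10 | 0.20 | 0.30 |
| 3 | 0.15 | 0.30 | 0.45 |

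On the percent scale, assume that the others fall by 3% on average and the k by d%. The understatement is k × (d − 3) / 20. It runs from 1 × 17 / 20 = 0.85 points (one person, 20% fall) to 3 × 37 / 20 = 5.55 points (three people, 40% fall).

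**Do these falls reach the 40% threshold?** Entry requires at least 10 g/dL (section 5.5). A fall above 40% means more than 0.40 × 10 = 4.0 g/dL at that minimum, and more than 4.8 g/dL from 12 g/dL. An excess of 3 g/dL is at most 30% of baseline, so the table says nothing about the count of falls above 40%.

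**The case against.** The strongest reply is that the protocol already protects the safety record. The event that triggers withdrawal is on the case report form, falls above 40% are reported separately, and discontinuations go to the DSMB with reasons. This stands. A reader might infer that haemolysis cases would vanish, or that a real rate of falls above 40% would be reported as zero. The documents do not support that: anyone withdrawn after crossing 40% is already counted. Only a person who leaves before crossing, with no later value captured, would be missed.

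Second, section 12.2.2 cites two studies designed for G6PD-deficient people that found no clinically relevant haemoglobin reductions. Large falls may therefore be rare, and the fall sizes above have no source in the protocol. This also stands. In addition, the median in section 7.2 is less sensitive than the means that the t-tests compare: dropping 1 to 3 of the largest fallers from 20 moves the median by only 0.5 to 1.5 ranks.

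Third, a reader might infer that withdrawals will differ by arm. That needs an unblinded clinician, and the sections conflict. A reader might also infer a threat to the primary outcome. That arises only if withdrawal comes before the day 2 feed, with one scheduled visit (day 1) in between, and nothing in the protocol allows an estimate of how often.

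Fourth, section 11.1 does not say how missing visits are handled, and a separate analysis plan may do so. That is fair as to method. It does not answer a rule that stops data collection.

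**Conclusion.** The point holds as a weakness in data collection. Section 8.2 permits an adverse event to end follow-up, and nothing elsewhere preserves the haemoglobin schedule for the people most informative about the major safety endpoint. The triggering event survives; what is at risk is the nadir, the crossing of 40%, recovery, and the comparisons up to day 28.

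The loss is possible, not certain, because withdrawal is discretionary. The direction is towards safety if those withdrawn have larger falls than those who remain. A between-arm comparison is biased only if the loss is unequal between the arms. With 1 to 3 people lost and an assumed excess fall of 1 to 3 g/dL, an arm's mean fall is understated by 0.05 to 0.45 g/dL at the visits concerned. If large falls are as rare as the cited evidence suggests, the effect will sit at the low end or be absent. The change is still worth making because it is cheap and because, with 20 per arm, each such participant carries weight.

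**What to change.** Amend the sentence in section 8.2. Clinical care and treatment decisions after an adverse event remain with the study clinician exactly as now, but an adverse event does not by itself end safety follow-up. Scheduled haemoglobin and adverse event assessments continue to day 28 unless consent is withdrawn, and these data enter the analysis. The larger research draws (feeding assays, MACS, plasma) stay subject to the clinician's judgement.

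Separately, reconcile sections 5, 5.3 and 8.4 on whether the clinician is blinded.

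The cost is one sentence and a few extra safety visits for participants who would otherwise have left. Haemoglobin needs 0.05 mL per visit (Table 6), so a participant leaving after day 2 would give 4 × 0.05 = 0.20 mL over days 7, 14, 21 and 28. Requiring the full schedule instead would cost 6.2 + 6.2 + 3.9 + 3.9 = 20.2 mL at most over the same visits, which is why the research draws are left out of the requirement.
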